5.2.1.2. Analysis Methods for the Primary Endpoint

The log rank test will be the primary method for the analysis of time to recurrence based on CEC confirmed events, stratified by the stratification variables for randomization. Analysis based on the ITT analysis set will be used as the primary analysis. Analysis based on the PP analysis set will be considered as a sensitivity analysis.

Time to recurrence will be summarized with the 25th, 50th (median), and 75th percentiles using the Kaplan-Meier (KM) method. The 95% confidence interval (CI) for the percentiles will be calculated using a log-log transformation. The percentage of subjects with pericarditis recurrence and its 95% CI will be calculated at weeks 8, 16, 24, and 36 since randomization, using Greenwood's formula with a log-log transformation.

The hazard ratio for KPL-914 vs. placebo and the corresponding Wald 95% CI will be calculated based on a Cox proportional-hazards model with treatment as covariate, stratified by randomization strata.

A sensitivity analysis will be performed based on the Investigator's judgement of pericarditis recurrence. A 2×2 table for the concordance/discordance between Investigator's judgement and CEC's adjudication will be generated.

Upon pericarditis recurrence as determined by the investigator, subjects who report at least 1 day with pericarditis pain measurement ≥ 4 on the 11-point NRS and have 1 CRP value ≥ 1 mg/dL (either on the same day or separated by no more than 7 days) will receive bailout rilonacept (2 open-label injections of 160 mg rilonacept [or 4.4 mg/kg for pediatric subjects]) irrespective of randomized treatment assignment and as soon as at least 5 days have passed since the last study drug injection. The subjects transitioning to bailout rilonacept will remain blinded to their randomized treatment assignment.

For subjects who have pericarditis recurrence, the frequency table and listing will be generated for the following treatment prescribed by the Investigator:

- Bailout rilonacept
- Analgesics
- NSAIDS
- Colchicine
- Other.

The following criteria for pericarditis recurrence were provided to CEC to determine pericarditis recurrence:

1. Re-appearance or worsening of typical pericarditis pain (with at least one pain NRS recording ≥ 4) AND elevated CRP (≥ 1.0 mg/dL) either on the same day or separated by no more than 7 days

OR

2. Re-appearance or worsening of typical pericarditis pain (with at least one pain NRS recording ≥ 4), AND abnormal CRP (> 0.5 mg/dL) either on the same day or separated by no more than 7 days AND at least 1 supportive evidence of pericarditis as below

OR

3. Re-appearance or worsening of typical pericarditis pain (but no NRS scores being ≥ 4), AND elevated CRP (≥ 1.0 mg/dL) not attributable to other causes AND at least 1 supportive manifestation of pericarditis as below.

Supportive Evidence (Pericarditis manifestations):

- increased WBC count $>$ upper limit of normal (ULN)
- fever $> 38^{\circ}\text{C}$
- presence of pericardial rub
- ECG changes consistent with pericarditis, i.e., findings of new widespread ST-segment elevation and/ or PR-segment depression
- new or worsened pericardial effusion on echocardiography (ECHO)
- new or worsening pericardial inflammation on MRI or other imaging modality.

The above information will be summarized and/or listed.

5.2.2. Secondary Efficacy Endpoint in the RW Period

This Section defines secondary efficacy endpoints for the RW period. Endpoints for the RI and LTE periods are defined in Section 5.2.3.

5.2.2.1. Definition of Major Secondary Efficacy Endpoints in the RW Period

This section defines 3 major secondary endpoints. These endpoints will be analyzed with the ITT Week 16 analysis set. Handling of missing data due to end of RW period will be discussed in Section 5.2.2.2.

1. Proportion of subjects who maintained clinical response at Week 16 of the RW period. clinical response is defined as a weekly average of daily pericarditis pain on the 11-point NRS ≤ 2.0 and CRP level ≤ 0.5 mg/dL, and on monotherapy of randomized study drug at Week 16.

Subjects who complete 16-week of double-blinded treatment and meet the clinical response criteria at Week 16 will be considered as responders. Subjects who had recurrence, discontinued double-blinded treatment, lost to follow-up, and used bailout riloncept or rescue medications (ORT or corticosteroid) before Week 16 will be considered as non-responders.

If either weekly average of NRS or CRP is missing at week-16 assessment, the subject will be considered as a non-responder.

2. Percentage of days with pain NRS ≤ 2 in the first 16 weeks of the RW period. No or minimal pain is defined as non-missing NRS ≤ 2 .

The denominator will be 112 (=16x7) for every subject. NRS assessments after treatment termination will be included. NRS assessments while on rescue medications for pericarditis will considered not meeting this criterion. Receiving each administration of bailout riloncept will disqualify for meeting NRS ≤ 2 for 7 days. Missing values will be counted as 0 day meeting the criterion.

3. Proportion of subjects with absent or minimal pericarditis symptoms (based on the 7-point PGIPS) at Week 16 of the RW period.

Subjects who do not have the assessment due to early termination or other reasons will be considered as not meeting the criterion. Subjects who took rescue medications at the Week 16 assessment or used bailout riloncept on or before Week 16 will also be considered not meeting the criteria.

5.2.2.2. Analysis Methods for Major Secondary Efficacy Endpoints in the RW Period

These endpoints will be analyzed with the ITT Week 16 analysis set.

1. For the proportion of subjects who maintained Clinical Response at Week 16 of the RW period, the response rate and Clopper–Pearson 95% CI will be obtained for each arm. Difference of response rate (KPL-914 – Placebo) and 95% CI based on normal approximation will be provided. The Cochran–Mantel–Haenszel (CMH) test will be used to test the treatment effect, stratified by the stratification variables for randomization.
2. For the percentage of days with pain NRS ≤ 2 in the first 16 weeks post randomization, an analysis of covariance will be used for treatment comparison. In addition to treatment arm, the following covariates will be included in this analysis: the stratification variables for randomization, and RI baseline NRS in 2 categories: NRS ≤ 2 versus NRS > 2 . LS mean difference and the 95% CI will be provided.
3. For proportion of subjects with absent or minimal pericarditis symptoms (based on the 7-point PGIPS) at Week 16 of the RW period, the response rate and Clopper–Pearson 95% CI will be obtained for each arm. Difference of response rate (KPL-914 – Placebo) and 95% CI based on normal approximation will be provided. The Cochran–

Mantel–Haenszel (CMH) test will be used to test the treatment effect, stratified by the stratification variables for randomization.

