Additionally, after the randomized withdrawal period has been closed when at least 22 confirmed recurrent pericarditis events have been accrued, subjects who have not yet completed the full 12 weeks of RI period at that time will be allowed to continue tapering of concomitant meds in the RI period; those subjects who achieved clinical response by Week 12 will be given the option to receive open-label rilonacept in the Long-term Extension Treatment period (LTE) without having to proceed through the RW period.

- **Double-blind placebo-controlled RW period** (pericarditis recurrence event-driven duration), during which subjects who were able to stop background SOC pericarditis therapy and who achieve clinical response at RI Week 12/RW baseline are randomized in a double-blind manner at a 1:1 ratio to the following:
 - Rilonacept 160 mg (2.2 mg/kg in pediatric subjects) SC injections once weekly
 - Matching placebo SC injections once weekly

Pericarditis Recurrence in the RW Period

Pericarditis recurrence is defined as the recurrence of typical pericarditis pain associated with supportive objective evidence of pericarditis. Upon pericarditis recurrence, subjects who report at least 1 day with pericarditis pain measurement ≥ 4 on the 11 point NRS and have 1 CRP value ≥ 1 mg/dL (either on the same day or separated by no more than 7 days) will receive bailout rilonacept (2 open-label injections of 160 mg rilonacept [or 4.4 mg/kg for pediatric subjects] followed by once weekly open-label rilonacept SC injections of 160 mg [or 2.2 mg/kg for pediatric subjects]) irrespective of randomized treatment assignment and as soon as at least 5 days have passed since the last study drug injection. Sequential oral rescue therapy (ORT), i.e., analgesics first, then NSAIDs, and then colchicine, can be added if needed at the discretion of the Investigator, as outlined in the protocol and Pharmacy Manual.

Subjects with pericarditis recurrence and who do not meet the protocol criteria for bailout rilonacept will continue blinded study drug until the protocol criteria for bailout rilonacept are met or through the end of the RW period. For those subjects, sequential ORT can be added to blinded study drug at the discretion of the Investigator, as outlined in the protocol and Pharmacy Manual.

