2.3. Sample Size Calculation and Randomization

2.3.1. Sample Size Calculation

Sample size calculation is based on the primary endpoint, time to pericarditis recurrence defined as the time from randomization to the date of the first pericarditis recurrence for each subject. Time to pericarditis recurrence is assumed to follow an exponential distribution. An event of interest is defined as a subject's first adjudicated recurrence of pericarditis. The following assumptions are used in the sample size calculation using EAST 6.4.1:

- 1-sided significance level: 2.5%
- Power: 90%
- Median time to event (in weeks) in placebo: 8
- Hazard ratio (rilonacept/placebo): 0.244
- Percentage of subjects in the RI period that will not reach RW: 10%.

Given these assumptions, a total of 22 adjudicated pericarditis recurrence events is required to achieve the power. About 25 subjects per arm (a total of 50 subjects) or more will be randomized. Considering 10% of subjects in the RI period that will not reach the RW period, approximately 56 subjects will be enrolled in this study.

Subject enrollment and the pericarditis recurrence event accrual will be closely monitored during the study. The monitoring activities will be done in a blinded fashion during the RW period. If the number of subjects randomized is less than 50 and/or the time anticipated for the number of events required for the analysis of primary efficacy endpoint significantly exceeds the projected timeline, additional subjects may be enrolled and/or randomized at Kiniksa Pharmaceutical's discretion. However, at this time it is anticipated that no more than 100 subjects will be enrolled into this study.

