4. ANALYSIS SETS

4.1. Intent-to-Treat (ITT) Analysis Set

All subjects who are randomized in the RW period will be included in the Intent-to-Treat (ITT) analysis set. The primary analysis for efficacy endpoints in the RW period will be based on the ITT analysis set unless otherwise specified. Treatment comparisons for all analyses will be based on each subject's treatment assignment from randomization.

The following analysis sets are defined for the analysis of secondary endpoints:

- ITT Week 24 analysis set: All subjects randomized at least 24 weeks before data cutoff will be included. This analysis set will be used for secondary efficacy endpoints measured at week 24 in the RW period.
- ITT Week 16 analysis set: All subjects randomized at least 16 weeks before data cutoff will be included. This analysis set will be used for secondary efficacy endpoints measured at week 16 in the RW period.
- ITT Week 8 analysis set: All subjects randomized at least 8 weeks before data cutoff will be included. This analysis set will be used for secondary efficacy endpoints measured at week 8 in the RW period.

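### The normal-approximation 95% CI for the Week 16 response-rate difference (major secondary endpoints 1 and 3) is poorly centred at the planned sample size, so its lower limit overstates the minimum benefit too often

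*SAP*

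**What the plan says.** SAP version 2.0, section 5.2.2.2, treats major secondary endpoint 1 (maintained clinical response at Week 16) and endpoint 3 (absent or minimal symptoms on the PGIPS at Week 16) alike:

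- Each arm's rate gets an exact interval: a Clopper–Pearson "95% CI will be obtained for each arm".
- For the difference, KPL-914 minus placebo, a "95% CI based on normal approximation will be provided".
- The CMH test "will be used to test the treatment effect, stratified by the stratification variables for randomization".

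Stratification is attached to the test only. The SAP does not call the interval unstratified, but a plain difference with a normal-approximation interval is the natural reading. Endpoint 2 uses ANCOVA and is not affected. Section 5.2.2.3 (items 1, 2, 5 and 6) carries the same method to the Week 24 and Week 8 versions.

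On size, section 2.3.1 says: "About 25 subjects per arm (a total of 50 subjects) or more will be randomized", and anticipates that "no more than 100 subjects will be enrolled into this study". Subjects "are randomized in a double-blind manner at a 1:1 ratio" (section 2.1). The analysis uses the ITT Week 16 set of section 4.1: "All subjects randomized at least 16 weeks before data cutoff will be included". The data cutoff is event-driven, at 22 or more adjudicated recurrences (section 2.4). The SAP states neither the size of the Week 16 set nor any expected response rate.

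**The concern.** The plan uses exact limits for each arm, then a large-sample interval for the treatment effect itself, in a set of at most a few dozen subjects per arm and with rates expected to be far apart. That interval is symmetric about the observed difference. When one rate is high and the other low, the sampling distribution of the difference is skewed, and a symmetric interval sits too far from zero.

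At stake is the reported effect size for two of the three alpha-controlled major secondary endpoints. The lower limit tells a reader how small the benefit could be. If it is too high more often than the stated 2.5%, the error favours the drug.

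**Working it through.** **1. The plan's own figures.** Section 2.3.1 lists "1-sided significance level: 2.5"%, 90% power and a hazard ratio of 0.244. Schoenfeld's formula gives 4 × (1.960 + 1.282)² / (ln 0.244)² = 42.03 / 1.990 = 21.1, so 22 events, as stated. Enrolment: 50 / 0.90 = 55.6, so 56, as stated.

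**2. Proxy rates at Week 16.** The sample-size model is exponential with a placebo median of 8 weeks. Recurrence-free at 16 weeks: placebo 0.5^(16/8) = 0.25; rilonacept 0.25^0.244 = 0.713. True difference 0.463.

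**3. Size of the Week 16 set (assumption).** Accrual is not in the SAP. With 50 planned, uniform accrual over an assumed 26 to 78 weeks and cutoff at the expected time of the 22nd event, about 10 to 13 per arm have 16 weeks of follow-up. A 4-week lag to cutoff gives 14 to 15. With 90 planned (100 enrolled less 10%) the figures are about 5 to 12 and 12 to 15. So 12 per arm is plausible, and 25 is the whole planned randomized set.

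**4. Exact coverage.** For n per arm, each pair (x₁, x₂) has probability Bin(x₁; n, 0.713) × Bin(x₂; n, 0.25).

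- Planned interval: p̂₁ − p̂₂ ± 1.96 √[p̂₁(1−p̂₁)/n + p̂₂(1−p̂₂)/n].
- Newcombe interval, with Wilson limits (l, u) for each arm: lower = p̂₁ − p̂₂ − √[(p̂₁−l₁)² + (u₂−p̂₂)²]; upper = p̂₁ − p̂₂ + √[(u₁−p̂₁)² + (p̂₂−l₂)²].

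Summing the probabilities of the pairs whose interval contains 0.463:

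| n per arm | Planned: coverage | Planned: lower limit above truth | Planned: mean width | Newcombe: coverage | Newcombe: mean width |
|---|---|---|---|---|---|
| 12 | 90.4% | 8.1% | 0.673 | 95.9% | 0.621 |
| 14 | 93.8% | 4.1% | 0.628 | 94.1% | 0.584 |
| 15 | 91.9% | 6.5% | 0.609 | 95.3% | 0.568 |
| 18 | 93.0% | 5.2% | 0.560 | 94.2% | 0.527 |
| 20 | 91.7% | 5.9% | 0.533 | 93.8% | 0.504 |
| 25 | 93.2% | 5.3% | 0.479 | 95.4% | 0.458 |
| 45 | 95.1% | 3.3% | 0.361 | 94.8% | 0.351 |

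From 12 to 25 per arm, the planned interval's misses on the other side (upper limit below the truth) are only 1.5 to 2.3%. Miettinen–Nurminen coverage is 93.9, 93.5, 95.1 and 94.6% at 12, 15, 20 and 25.

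**5. Why it is centring.** Take 9/12 against 3/12. The planned interval is 0.50 ± 1.96 × √(2 × 0.1875/12) = 0.50 ± 0.346, that is 0.154 to 0.846. The Wilson limits are 0.468 to 0.911 and 0.089 to 0.532, so Newcombe gives 0.50 − √(2 × 0.282²) = 0.101 to 0.50 + √(2 × 0.161²) = 0.728. Newcombe is shorter (0.627 against 0.693) and lies closer to zero.

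**6. Other rates.** Over a grid of 50–95% against 10–40%, mean coverage at 12, 16, 20 and 25 per arm is 91.2, 92.2, 92.8 and 93.1% for the planned interval (lowest 80.5%), against 94.4, 94.6, 94.6 and 94.7% for Newcombe (lowest 91.2%). At 45 per arm the means are 94.1 and 94.7%.

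**7. Limits above 100%.** At the proxy rates the planned upper limit exceeds 100% in 6.8% of trials at 12 per arm and almost never at 25 (0.02%). At 90% against 20% the figures are 41% and 4%.

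**The case against.** Much of the case for the plan stands.

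- **No inferential consequence.** Under section 3.3 significance follows from the test p-values, and for endpoints 1 and 3 that is the CMH test. Type I error is unaffected.
- **A crude difference beside a stratified test is common.** A reader might infer that interval and test contradict each other. The SAP does not support that: the interval describes the crude difference next to crude arm rates, and section 3.2 may pool strata or drop stratification from the test. The two can disagree in a given trial, but how often depends on strata shares that the SAP does not give.
- **The interval is not too narrow.** A reader might infer this from the low coverage. At the proxy rates it is wider on average than Newcombe's at every size in the table. Newcombe is wider only when a rate nears 100%.
- **Coverage oscillates.** The 90.4% at 12 per arm is a trough; at 14 per arm the two methods hardly differ (93.8% and 94.1%). At 90% against 20% with 20 or 25 per arm the planned interval covers better (94.1 and 94.3%, against 92.3 and 92.6%). The lowest grid values come from extreme rates.
- **The inputs are partly assumed.** The plan allows more than 25 per arm, and 12 is not an SAP figure. The 25% and 71% are recurrence-free rates, whereas endpoint 1 also needs pain, CRP and monotherapy criteria and endpoint 3 is a PGIPS rating.

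What these points do not remove is the one-sided miss. At the proxy rates the lower limit is too high in more than 4% of trials at every size from 12 to 25 per arm in the table, including n = 14.

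**Conclusion.** The point holds as a fault in the reported effect estimate, not in the test. At 12 to 25 per arm (assumed) and 71% against 25% (proxy), the nominal 95% interval covers about 90 to 94%, and its lower limit lies above the true difference in about 4 to 8% of trials instead of 2.5%. At 25 per arm the shortfall in coverage is about 2 points (93.2%) and the lower-limit miss is about twice nominal (5.3%). By 45 per arm coverage at these rates is close to nominal. An upper limit above 100% matters only with small n and high response rates. The Week 8 and Week 24 versions use the same method, but their coverage was not computed; their set sizes and rates differ.

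**What to change.** In section 5.2.2.2, for endpoints 1 and 3, replace the normal-approximation interval with a Newcombe or Miettinen–Nurminen 95% CI, stratified with the same strata and the same section 3.2 pooling rule as the CMH test, and unstratified if that rule drops stratification. Section 5.2.2.3 then carries the change to Weeks 8 and 24.

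Costs and limits:

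- One sentence in the SAP and slightly more programming.
- Strata with an empty arm need a stated rule. Section 3.2 triggers on a uniform response, not on an empty arm. In a simulation with assumed strata shares of 45, 40, 10 and 5%, about 1.3 subjects per trial at 12 per arm fell in such strata and dropped out of the stratified Newcombe estimate. Coverage was about 94%, with mean width 0.652 against 0.673 for the planned interval.
- The interval is marginally wider only when a rate nears 100%; otherwise it is similar or narrower.
- Coverage improves on average, not in every case. Newcombe's own misses fall mostly on the other side, with the upper limit too low, so they do not overstate the minimum benefit.

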3. GENERAL STATISTICAL CONSIDERATIONS

3.1. General Methods

Statistical analysis will be performed using SAS® software Version 9.4 or later. Continuous variables will be summarized using the mean, the standard deviation, median, minimum value, and maximum value. Time-to-event variables will be summarized using percent censored, event rate, and 25th, 50th, and 75th percentiles with 95% CI, if estimable. Categorical variables will be summarized using frequency counts and percentages. Data will be listed in data listings.

At RI, RW, and LTE periods, baseline will be the last value before the first dose of study drug within each individual period unless otherwise specified. For change-over-time endpoints in the RW period, by-visit analysis will be performed at each scheduled visit for at least 24 weeks.

When weekly average of NRS is used, it will be calculated based on every 7 days starting on the day after the first injection in each period. If there are missing values during the 7- day period, the average will be calculated based on the non-missing values. If 50% or more values (≥ 4 days) are missing, the average value will be set to missing.

By-visit analyses will be based on nominal visits and observed data, with unscheduled visits excluded.

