5.1.3. Baseline Disease Characteristics

Baseline disease characteristics include the following:

- Oral corticosteroid use at RI Baseline (yes/no)
- Diagnosis of recurrent idiopathic pericarditis at RI (yes/no)
- Type of recurrent Pericarditis
 - Idiopathic
 - Pericardiotomy syndrome
 - Dressler's syndrome
 - Still's disease
 - Other
- Duration of disease from first episode to the date of informed consent
- Total number of pericarditis episodes, total number of episodes in the past year until first injection in the RI period, and annualized number of episodes per year,
- Time since beginning of qualifying episode in days
- Baseline central CRP value and weekly pain NRS score
- Baseline pericardial rub, effusion, tamponade, electrocardiogram (ECG) findings (widespread ST-elevation and PR-Depression), ECG interpretation
- Pericarditis treatment at baseline
 - Analgesics
 - Non-opioid analgesics
 - Opioid analgesics
 - Nonsteroidal anti-inflammatory drug (NSAIDs)
 - Aspirin

- Other NSAIDs
- Colchicine
- Corticosteroids
 - Oral corticosteroids
 - IM/IV corticosteroids
- Other

Disease characteristics for the qualifying episode, including the following:

- Number and proportion of subjects with presence of pericarditis pain, pericardial rub, new widespread ST-segment elevation or PR-segment depression on ECG, new or worsening in pericardial effusion, and pericardial inflammation on magnetic resonance imaging (MRI).
- Values of pain level, CRP (mg/dL), fever (Celsius), white blood cell (WBC; $10^3/\mu\text{L}$), and erythrocyte sedimentation rate (ESR) (mm/hr).
- Treatment for the qualifying episode
 - Analgesics
 - Non-opioid analgesics
 - Opioid analgesics
 - Nonsteroidal anti-inflammatory drug (NSAIDs)
 - Aspirin
 - Other NSAIDs
 - Colchicine
 - Corticosteroids
 - Oral corticosteroids
 - IM/IV corticosteroids
 - Other

The categorical (discrete) variables will be summarized using counts and percentages. The continuous variables will be summarized using n, mean, median, standard deviation, and range (minimum, maximum). Summaries will be presented for the RI, RW, and LTE periods.

Baseline disease characteristics will also be summarized for subjects who are on corticosteroid at RI baseline. In addition to those specified above, the following baseline data will be summarized:

- Duration (in weeks) of using oral corticosteroid prior to enrollment
- Average dose (mg/day) of oral corticosteroid prior to enrollment

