5.2.2.3. Other Secondary Efficacy Endpoints in the RW Period and Statistical Method

All time-to-event endpoints start from the day of randomization. The same censoring rules for the primary endpoint will be applied. Missing values will not be imputed unless otherwise specified. Analysis of secondary endpoints will be based on ITT analysis unless otherwise specified.

1. Proportion of subjects who maintained Clinical Response at Week 24 of the RW period based on ITT Week 24 analysis set

The same rules and method for the first major secondary endpoint will be applied, except that 16 weeks is replaced with 24 weeks.

2. Proportion of subjects who maintained Clinical Response at Week 8 of the RW period based on based on ITT Week 8 analysis set

The same rules and method for the first major secondary endpoint will be applied, except that 16 weeks is replaced with 8 weeks.

3. Percentage of days with minimal or no pain in the first 24 weeks post randomization based on ITT Week 24 analysis set

The same rules and method for the second major secondary endpoint will be applied, except that 16 weeks is replaced with 24 weeks.

4. Percentage of days with minimal or no pain in the first 8 weeks post randomization based on ITT Week 8 analysis set

The same rules and method for the second major secondary endpoint will be applied, except that 16 weeks is replaced with 8 weeks.

5. Proportion of subjects with absent or minimal pericarditis symptoms (based on the 7-point PGIPS) at Week 24 of the RW period based on subjects who were randomized at least 24 weeks before data cutoff

The same rules and method for the third major secondary endpoint will be applied, except that 16 weeks is replaced with 24 weeks.

6. Proportion of subjects with absent or minimal pericarditis symptoms (based on the 7-point PGIPS) at Week 8 of the RW period based on subjects who were randomized at least 8 weeks before data cutoff

The same rules and method for the third major secondary endpoint will be applied, except that 16 weeks is replaced with 8 weeks.

7. Proportion of subjects without pericarditis recurrence in the first 24 weeks of the RW period

The proportion of subjects without pericarditis recurrence in the first 24 weeks of the RW period in each arm will be estimated using the KM method, as described in the

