5.2.3.1. Secondary Endpoints in the RI Period

The following efficacy endpoints will be included for the RI period. Unless specified otherwise, change means change from RI baseline to RI week 12, and the denominator for a proportion is the total number of subjects who were treated in the RI period.

1. Time to pain response, defined as number of days from first dose to the first day a subject’s daily pain NRS is ≤ 2 of the 3 days over which, the rolling average daily pain NRS is ≤ 2 . Subjects with baseline NRS ≤ 2 will be excluded from the analysis. If one or more daily NRS score is missing, rolling average will be considered not meeting the response criteria.
2. Time to CRP normalization (≤ 0.5 mg/dL)

Time to CRP normalization will be censored at treatment discontinuation, taking prohibited medication, or week 12, whichever occurs first. Subjects with baseline CRP ≤ 0.5 mg/dL will be excluded from the analysis.

3. Time to riloncept monotherapy

Time to riloncept monotherapy is defined as number of weeks from first dose to the first day of achieving monotherapy. Subjects without background therapies at RI baseline will be excluded from the analysis.

4. Time to treatment response defined as time from first dose to the first day of pain response (defined in endpoint 1 above), and CRP ≤ 0.5 mg/dL within 7 days before or after pain response. Treatment response day will be the day of pain response, whether pain response occurs before or after CRP ≤ 0.5 mg/dL.
5. Proportion of subjects achieving clinical response at RI week 12 based on RIS analysis set

Subjects who stopped background SOC pericarditis therapy on or before week 10, as well as who achieve CRP ≤ 0.5 mg/dL and weekly average of daily pericarditis pain score ≤ 2.0 on the 11-point NRS within the 7 days prior to and including the day of randomization on RI Week 12/Randomization are responders.

Additional analysis will be done base done the completers who finished the 12-weeks of RI treatment.

6. Number (percentage) of subjects with normalization of CRP (≤ 0.5 mg/dL) at RI Week 12. Subjects with baseline CRP > 0.5 mg/dL in the RI analysis set will be used in the analysis.
7. Change from baseline in pericarditis weekly pain score at RI Week 12 and over time.
8. Change from baseline in CRP level at RI Week 12 and over time.
9. Proportion of subjects with resolution of echocardiographic and ECG abnormalities (yes/no) at RI Week 12.

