c Full physical examination includes at minimum evaluation of vital signs, head, eye, ear, nose, and throat as well as cardiovascular, dermatological, musculoskeletal, respiratory, GI, genitourinary, and neurological systems. The decision to perform examination of genitourinary system should be guided by clinical judgement.

d Abbreviated physical examination includes at minimum evaluation of vital signs, lung and heart sounds, including evaluation for pericardial rub.

e ECHO is required to be obtained according to the central core lab parameters and then read locally and submitted to the central core lab for separate review and analysis.

f Both a documented CRP ≥ 1.0 mg/dL AND a pericarditis pain level of ≥ 4 is required 7 days prior to and including the Run-In Baseline visit. These are not required to occur on the same day.

g Subjects missing ≥ 4 daily pain measurements during the 7 days prior to and including the Randomization Withdrawal baseline visit will be unable to proceed to randomization due to lack of data required for treatment response evaluation.

h Lipid panels are non-fasting and are to be drawn at a minimum of every 6months during the randomization withdrawal and LTE periods, or more frequently as needed, with mandated evaluations as detailed in the schedule of events.

i Applicable to 24-hour post dose PK sub-study participants only.

j For women of child bearing potential - urine pregnancy testing can be repeated as needed throughout the course of the study and serum pregnancy can be drawn as needed; urine pregnancy is required to be performed at enrollment and 6 weeks after the last dose of study drug.

k Pharmacogenomics informed consent and subsequent sampling can be performed at any time in the study however, it is preferable to have this completed at the beginning of the study.

l Adverse event reporting begins following the subject providing informed consent.

m All procedures are to be completed prior to study drug administration.

Statistical Analysis Plan

Kiniksa Pharmaceuticals, Ltd.
Study KPL-914-C002

-
- n The first dose of study drug is a loading dose. Adult subjects receive 2 SC doses 160 mg (total 320 mg); pediatric subjects (subjects ≥ 12 and < 18 years of age) receive 2 SC doses of 2 x 2.2 mg/kg.
 - o Study drug administration is once weekly with a minimum of 5 days required between doses.

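### The pain-days ANCOVA enters run-in baseline NRS only as ≤2 versus >2, which probably discards much of the score's information; a continuous score costs no extra degree of freedom

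*SAP*

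**What the plan says.** SAP version 2.0, Section 5.2.2.2 item 2, analyses the percentage of days with NRS ≤2 over 16 weeks by ANCOVA. Besides treatment arm, the covariates are "the stratification variables for randomization, and RI baseline NRS in 2 categories", namely ≤2 and >2. For the Week 24 and Week 8 forms of the endpoint (Section 5.2.2.3, endpoints 3 and 4), the SAP states that "The same rules and method for the second major secondary endpoint will be applied".

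Four other places bear on how many subjects can fall in the ≤2 category:

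- Section 13.1, Table 4, footnote f: besides a raised CRP, "a pericarditis pain level of ≥ 4 is required 7 days prior to and including the Run-In Baseline visit". Of the pain and CRP values it adds: "These are not required to occur on the same day".
- Section 3.1: unless otherwise specified, "baseline will be the last value before the first dose of study drug within each individual period".
- Section 5.2.3.1, endpoint 1 (time to pain response in the run-in): "Subjects with baseline NRS ≤ 2 will be excluded from the analysis".
- Section 5.1.3 lists, among the baseline disease characteristics, "Baseline central CRP value and weekly pain NRS score".

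Section 3.3 places the Week 16 endpoint in the Hochberg step of the confirmatory hierarchy. Section 2.3.1 plans about 25 randomized subjects per arm. Section 4.1 limits the Week 16 set to those randomized at least 16 weeks before cutoff, so the analysed number may be smaller.

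**The concern.** The cut at 2 lies well below the pain level of 4 that qualified a subject for entry. If most subjects are on the same side of it, the covariate says little about differences in pain between them: a subject at 3 and a subject at 9 are treated alike. Adjustment for baseline is meant to reduce residual variance, and with about 50 subjects in a confirmatory test any reduction that costs nothing is worth having. The 11-point score is already recorded, so the detail is given up by the way the covariate is coded and not by a lack of data.

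What is at stake is precision for this endpoint at Weeks 8, 16 and 24. The validity of the test is not in question.

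**Working it through.** **The plan's own figures.** The SAP's only sample-size calculation is for the primary endpoint. It reproduces: (z₀.₉₇₅ + z₀.₉₀)² / (0.25 × ln(0.244)²) = 21.12, rounded up to 22 events; 50 / 0.90 = 55.6, so 56 enrolled. No power or variance figure is given for the pain-days ANCOVA, so the shares and effects below are assumptions shown as ranges.

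**Step 1. Does the entry rule force baseline NRS above 2?** No.

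- Under the last-value definition, the qualifying reading may fall on any day of the 7-day window, and the last pre-dose reading can be lower.
- Under a weekly average, one day at 4 and six at 0 gives 4/7 = 0.57. The average is ≤2 whenever the other six days average no more than (14 − 4)/6 = 1.67.

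The rule makes the >2 category likely to dominate but sets no limit on the ≤2 share.

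**Step 2. Information kept by the cut.** If the score is normal and linearly related to the outcome, cutting it at lower-tail share q keeps a fraction φ(z_q)² / [q(1 − q)] of the variance it would explain. For q = 0.02: z = −2.054, φ = 0.0484, and 0.0484² / 0.0196 = 0.12. For q = 0.30: z = −0.524, φ = 0.3477, and 0.3477² / 0.21 = 0.58.

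**Step 3. What the two-category covariate can itself explain.** Let d be the outcome difference between the two categories in residual SDs, taken from 0.2 to 0.8. Then R² = q(1 − q)d² / [1 + q(1 − q)d²]. With n = 50 and four other parameters (intercept, arm, two stratification variables), adding the covariate multiplies the residual variance by (1 − R²) × 46/45.

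| Assumed share ≤2 (of 50) | Share of explained variance kept | R², d = 0.2 to 0.8 | Change in residual variance |
|---|---|---|---|
| 2% (1) | 12% | 0.1% to 1.2% | +2.1% to +1.0% |
| 4% (2) | 19% | 0.2% to 2.4% | +2.1% to −0.2% |
| 10% (5) | 34% | 0.4% to 5.4% | +1.9% to −3.3% |
| 20% (10) | 49% | 0.6% to 9.3% | +1.6% to −7.3% |
| 30% (15) | 58% | 0.8% to 11.8% | +1.4% to −9.9% |

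With one or two subjects at ≤2, the lost degree of freedom roughly cancels whatever is gained. With 20% to 30%, the two-category covariate can be useful.

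**Step 4. Two categories against a continuous score.** Both use one degree of freedom, so the residual-variance ratio is (1 − kept × ρ²) / (1 − ρ²), where ρ is the correlation of baseline pain with the outcome within arms. With ρ = 0.3 assumed, ρ² = 0.09:

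- 2% share: (1 − 0.0108) / 0.91 = 1.087
- 10% share: (1 − 0.0308) / 0.91 = 1.065
- 30% share: (1 − 0.0518) / 0.91 = 1.042

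So the two-category form would leave residual variance about 4% to 9% higher at ρ = 0.3, and no higher if ρ = 0.

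**The case against.** A reader might infer that the covariate is almost constant, since entry needed pain of at least 4. The documents do not support that. Step 1 shows that a baseline of 2 or less is possible under either definition, and the exclusion rule in Section 5.2.3.1 shows that the SAP expects some such subjects. No share is stated anywhere.

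The cut is also not arbitrary. It is the threshold that defines no or minimal pain in the endpoint itself, so separating subjects already at that level before treatment is a recognisable choice. The model is prespecified and its test is valid. An imprecise covariate coefficient is a nuisance term and does not by itself disturb the treatment estimate; the cost of a useless covariate is one degree of freedom, 46/45, or about 2% of residual variance.

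The figures in Steps 2 and 4 assume normality and linearity, which a bounded score in patients selected for recent pain may not satisfy.

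Nor should pain at randomization be put forward as the obviously better covariate. Section 2.1 requires a weekly average of no more than 2.0 to be randomized, so that score is confined to 0–2 by design and its gain is unknown.

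All of this stands and keeps the point small. What remains is that a two-category version of an available 11-point score usually carries less information than the score: under the normal assumption, even a cut at the median keeps only about 64%.

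**Conclusion.** The point holds as a minor improvement in efficiency. The >2 category is likely to dominate, and the two-category covariate then probably discards much of what baseline pain could contribute: about 12% to 58% of the explained variance is kept for ≤2 shares of 2% to 30%, under an assumed normal score. The absolute gain from a continuous score cannot be stated, because the SAP gives neither the share nor the correlation. No bias, type I error inflation or loss of a stated power is shown, and the plan is not invalid as it stands.

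**What to change.** In Section 5.2.2.2 item 2, replace the two-category covariate with run-in baseline NRS as a continuous score, and say that it is the last value before the first run-in dose, as Section 3.1 defines baseline. Stating this also removes any doubt raised by the weekly pain score listed in Section 5.1.3. Apply the same wording to Section 5.2.2.3 endpoints 3 and 4, so that Weeks 8, 16 and 24 agree.

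The cost is one line of SAP text. The data are already collected and the model still spends one degree of freedom on baseline pain. Adding the weekly average NRS at randomization, also continuous, is optional: it would cost one further degree of freedom, its range is restricted to 0–2, and its benefit is unknown.
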